It is well-known that insulin requirements change during pregnancy and hence participants who are female and of childbearing age will have a urine pregnancy test done at screening and prior to each intervention. Participants will be excluded from the study if they are pregnant or planning pregnancy within the study time frame, to minimise any potential risk.

It is acknowledged that the clinical schedule is demanding of subject's time and includes overnight visits. This inconvenience is necessary to adequately and safely ensure participants receive the appropriate training on how to use the device and we will minimise the burden as much as possible by providing entertainment (TV, radio, reading material, internet access) in a comfortable environment with privacy. We will also ensure to make every effort to schedule visits around participants' lifestyles.

Research participants will benefit from being in the study by having increased access to diabetes professionals and more frequent visits to hospital with an emphasis on improved glycaemic control. They will also have the opportunity to use continuous glucose monitoring and review the results with a consultant diabetologist experienced with monitoring. The benefits to people with T1DM include the potential to carry forward technology to improve the risks of high glucose concentration leading to complications and distressing low glucose values.

Route of administration, dosage, dosage regimen, and treatment period

Insulin will be administered subcutaneously or intraperitoneally (in those who already have IP access with a DiaPort). This is the standard route of administration for insulin in T1DM. Alternative routes of administration include intravenous or inhaled. Intravenous insulin is used clinically in people with diabetes who are acutely unwell or those unable to eat and drink, inhaled insulin is no longer commercially available in the UK. The insulin dosage will be expressed as units infused subcutaneously as microboluses and will be calculated by the control algorithm of the closed-loop at 5-minute intervals. The treatment periods are defined by time spent in closed-loop insulin delivery.

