- Continuous glucose monitoring (Dexcom) will be connected according to manufacturer's instructions. Participants will be shown how to insert the sensor themselves and written instructions on how to calibrate the CGM every 12 hours and sensor change every 7 days as per manufacturer's instructions will be provided. Participants will be asked to wear the CGM for 2 weeks in total.
- Participants will be provided with the study pump and receive training on how to use it.
- Mixed methods psychological assessment: Diabetes quality of life (DQOL), Diabetes Treatment Satisfaction Questionnaire (DTSQ) and PAID Questionnaire to be completed. Semi-structured interviews by the investigators will be carried out.

Visit 2: CGM review

- 14 days following visit 1
- Remove CGM, upload data and review results with the participant.
- Make adjustments to insulin: carbohydrate ratio(ICR), insulin sensitivity factor (ISF), insulin basal infusion rates if necessary.

Randomisation:

The order of the three intervention arms will be completely randomised using sealed envelope (www.sealedenvelope.com).

Irrespective of which intervention the participants are allocated to for the first 6 weeks they will spend the first 24 hours at the clinical research facility for education and training on how to use the BiAP system as a whole (as outlined under visit 3).

Visit 3: 24 hours in clinic and start of 1st 6-week intervention period

- Attend the CRF at 16:00 until next day at 18:00.
- Participant will be connected to the BiAP system at 17:00.
- Finger prick blood sampling will be done eight times (before after each meal, bettime, one random during night) and analyzed immediately for glucose concentration using a standard glucometer.

- Standardized meals will be provided at 19:00 (dinner), 07:00 (breakfast) and 12:00 (lunch).
- The research team will ensure that the participants are comfortable with the BiAP system, particularly in the following situations:
- > How to switch the system from open-loop to closed-loop and vice versa.
- > When to calibrate the CGM system.
- When to seek help.
- Should the participant want a snack overnight they can record the carbs on the smartphone. For snacks of 15g or below participants will be advised not to bolus, but in cases of larger snacks they can calculate the bolus using the meal announcement button on BiAP/smartphone. Participants will be shown how to do this.

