- They will be free to go home at 18:00 with the BiAP device to continue the remaining 6 weeks.
- Participants will be trained to use the sensor, controller and insulin pump.
- They will have a structured education refresher.
- All training will be delivered by the study team and will be supported with written information. Participants will be expected to be able to self-manage the sensor, controller and pump prior to leaving the clinical research facility and competencies will be clearly recorded. Videos to support sensor insertion, and pump cannula and reservoir operations will be provided to all participants via email or on a USB stick and can be uploaded to participants' smartphones for off-line use. Contact details for clinical and technical support will be provided.
- The study team will phone the participants on day 1, day 3, day 7 and at 3 weeks.

Visit 4: End of first 6-week intervention period

- Attend the clinical research facility.
- Review any issues with the technology used.
- Download data from the study pump (the pump stores data for 90 days).
- Provide consumables (sensors, transmitter, insulin infusion sets) for the next 6-week intervention period.
- Gold score
- Mixed methods psychological assessment: Diabetes quality of life (DQOL), Diabetes Treatment Satisfaction Questionnaire (DTSQ) and PAID Questionnaire to be completed. Semi-structured interviews by the investigators will be carried out.
- Acceptability questionnaire to be completed.
- Repeat urine pregnancy test in female participants of childbearing age

• Participants will be instructed to revert back to their usual care for 2 weeks (wash-out period) before commencing the next intervention for 6 weeks.

Visit 5: End of 2nd 6-week intervention period

- Attend the clinical research facility.
- Review any issues with the technology used.
- Download data from the study pump.
- Provide consumables (sensors, transmitter, insulin infusion sets) for the next 6-week intervention period.
- Gold score
- Mixed methods psychological assessment: Diabetes quality of life (DQOL), Diabetes Treatment Satisfaction Questionnaire (DTSQ) and PAID Questionnaire to be completed. Semi-structured interviews by the investigators will be carried out.
- Acceptability questionnaire to be completed.
- Repeat urine pregnancy test in female participants of childbearing age

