- Participants will be instructed to revert back to their usual care for 2 weeks (wash-out period) before commencing the next intervention for 6 weeks.

Visit 6: End of 3rd 6-week intervention period and end of study

- Attend the clinical research facility.
- Review any issues with the technology used.
- Gold score
- Mixed methods psychological assessment: Diabetes quality of life (DQOL), Diabetes Treatment Satisfaction Questionnaire (DTSQ) and PAID Questionnaire to be completed. Semi-structured interviews by the investigators will be carried out.
- Acceptability questionnaire to be completed.
- Participants will be asked to return all components of the study device and will be instructed to revert back to their usual care.

Activity / Visit no	1	2	3	4	5	6	Additional information
Insertion of CGM sensor	X						Participants will change the sensor every week at home throughout the study
CGM review with participant		х					
Randomisation + Initialise the			Х	Х	Х		

Table: Overview of activities at each visit for participants

intervention/control							
Update CBR algorithm with new							This will be done automatically in
cases							the BiAP+ABC4D intervention
Clinical examination	x						
Weight measurement	x						
Venous blood test	Х						
Urine test	Х			Х	Х		
Pregnancy test (if applicable)	Х						
ECG	Х						
Questionnaire/s	Х			Х	Х	Х	
Follow-up clinical visits		Х	Х	Х	Х	Х	
Overnight stay in clinical			х				
research facility							
Semi-structured interview	Х			х	х	х	

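### Arm order is randomised with no stated balance and no period term is planned, although only period 1 is described as opening with training: a small, cheaply recovered loss of precision, not a bias

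*Combined protocol and SAP*

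**What the plan says.** Section 2.0 (Trial Design and Population) describes an open-label, three-period crossover of three arms in 20 participants, so there are six possible orders. Under the Randomisation heading that follows Visit 2: "The order of the three intervention arms will be completely randomised using sealed envelope". No blocking, Latin square or other balance over orders is mentioned.

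The same paragraph says that, whichever arm comes first, "they will spend the first 24 hours at the clinical research facility for education and training on how to use the BiAP system". Visit 3 then states: "Participant will be connected to the BiAP system at 17:00". It adds a structured education refresher and phone calls at days 1, 3 and 7 and at 3 weeks. Visits 4 and 5 list a technology review, data download, consumables and a two-week wash-out, with no further training. In the overview table the row beginning "Overnight stay in clinical" is marked at Visit 3 only.

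Section 3.0 plans three pairwise comparisons, corrected for multiplicity. It names the paired t test as the basis of the power calculation and gives no period or sequence term.

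**The concern.** Period 1 is set up differently from periods 2 and 3, so a learning or training effect on % time in target is plausible, though nothing in the documents gives its size. An analysis of raw paired differences leaves such an effect in the residual. With unrestricted randomisation of 20 people over six orders, the arms can also differ noticeably in how often each one falls in period 1.

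What is at stake is precision at the smaller of the plan's two differences. Section 3.0 anticipates 6 points for the adaptive against the fixed bolus calculator, where power is modest and there is little to spare. At the 12 points used for sizing there is ample power either way.

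**Working it through.** **Inputs from section 3.0.** n = 20; SD of the paired difference 9.9, given for each contrast; differences of 6 and 12 points.

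**Assumptions.** Two-sided Bonferroni alpha 0.05/3 = 0.0167 (the plan states neither the correction method nor the sidedness); no dropout unless stated; no carry-over; unrestricted randomisation as the reading of the plan; a period-1 step e of 0, 1, 3 or 5 points.

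**The plan's own figure.** A paired t test at 12 points has noncentrality 12/(9.9/√20) = 5.42 on 19 df, giving power 99.5%. Thirteen participants would suffice for 90%. The stated 20 participants and 90% are therefore not reproduced by the formula named. That is a separate matter, and the working below does not depend on it.

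**Unadjusted paired t, unrestricted orders.** For arms A and B, the step adds +e, −e or 0 to a participant's difference, each with probability 1/3, so the variance rises by (2/3)e². The SD is √(98.01 + (2/3)e²) on 19 df.

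| Step e | SD | Power at 6 | Power at 12 |
|---|---|---|---|
| 0 | 9.90 | 54.4% | 99.5% |
| 1 | 9.93 | 54.1% | 99.5% |
| 3 | 10.20 | 51.5% | 99.3% |
| 5 | 10.71 | 46.9% | 98.7% |

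Simulated type I error is 1.66% to 1.79% across these steps, against a nominal 1.67%.

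**Period-adjusted analyses.** Two versions were evaluated, averaging over random allocations. Their power does not depend on the period effect.

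- *Separate variances:* each paired difference is regressed on an intercept and two period contrasts, leaving 20 − 3 = 17 df.
- *Common variance:* one model with participant, period and treatment, leaving 60 − 20 − 2 − 2 = 36 df. Every contrast is taken to have SD 9.9, as in the plan.

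| Analysis | Orders | Variance inflation | Power at 6 | Power at 12 |
|---|---|---|---|---|
| Separate | near-balanced | 1.008 | 53.1% | 99.4% |
| Separate | unrestricted | 1.126 | 48.4% | 98.6% |
| Common | near-balanced | 1.004 | 58.0% | 99.7% |
| Common | unrestricted | 1.057 | 55.6% | 99.6% |

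With balanced orders, the separate-variance version breaks even with the unadjusted test at a step near 2 points. It loses 1.3 points at e = 0 and gains 6.2 at e = 5. At 12 points the largest gains, at e = 5, are 99.4 − 98.7 = 0.7 (separate) and 99.7 − 98.7 = 1.0 (common).

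Balancing without adjusting does not help the test. At e = 5 its power at 6 points stays at 46.7% and its type I error falls to 1.06%, because the period variation remains in the estimated error.

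**Chance imbalance.** The share of participants with arm A first minus the share with arm B first has a 95% limit of 0.35 under simple randomisation and a maximum of 0.10 under near-balance. Multiplied by the step:

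- e = 3: 0.35 × 3 = 1.05 points, against 0.10 × 3 = 0.3.
- e = 5: 0.35 × 5 = 1.75 points, against 0.10 × 5 = 0.5.

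With two random dropouts the limits are 0.389 and 0.167, that is 1.17 against 0.50 points at e = 3.

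**The case against.** The best case against acting is that randomised order already protects the comparison, the documents give no period effect, and pump training, the two-week CGM run-in and the wash-outs may keep any effect small. This largely stands. With no period effect the separate-variance adjustment loses about a point of power, and at 12 points almost nothing changes. The randomisation service may also apply blocks that the text does not mention. Later training stays cannot be wholly excluded either: section 1.0 says the schedule "includes overnight visits", in the plural, and the study-design figure is not shown.

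Three stronger readings are tempting but unsupported.

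- *The treatment contrasts are biased.* They are not: a period effect common to all arms averages out over random orders, and type I error holds.
- *Control-first participants are exposed to closed loop.* Visit 3 ends with "They will be free to go home at 18:00 with the BiAP device to continue the remaining 6 weeks", with no exception for sensor-augmented pump. But the training covers "How to switch the system from open-loop to closed-loop and vice versa" and the control arm is itself described as open-loop, so they may have gone home in open loop. Even if closed loop ran throughout the stay and those hours counted, this is 25 of 1,008 hours. With 7 of 20 starting on control and an assumed 20-point difference that day, the control mean moves 25/1008 × 20 × 7/20 = 0.17 points.
- *The arm is redrawn at each period.* The table row "Randomisation + Initialise the" is marked at Visits 3, 4 and 5, but it combines randomising with initialising an arm, and an arm is initialised three times.

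The last two are therefore requests to clarify, not demonstrated contradictions.

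**Conclusion.** The point holds as an optional improvement in precision. Nothing in the plan makes the primary comparisons invalid. At 6 points, balance plus a period term gives 53% or 58% power, depending on the variance assumption, whatever the period effect. The unadjusted test falls from 54% to 47% as the assumed step rises from 0 to 5.

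The common-variance figure relies on the plan's single SD of 9.9 holding for every contrast. If variances differ, that model can mislead. With assumed SDs of 9.9 for the control contrasts and 7 for the two closed-loop arms against each other, its type I error for the control contrasts was about 2.7% against 1.67%. Separate variances are therefore the robust choice, at about 1 power point when there is no period effect. A reader might infer that the common-variance model must be avoided, or that a period term is harmful without balanced orders. Neither holds in general: the first depends on unequal variances that the plan does not state, and the second is true only of the separate-variance version (48% unbalanced, against 56% for the common-variance model).

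**What to change.** 1. State that each participant's full order is drawn once, from a concealed list near-balanced over the six sequences, with the details of list generation held in a restricted document.
2. State that the three pairwise differences in % time in target come from a within-participant analysis with period and treatment terms, keeping the multiplicity correction. Say in advance whether variances are separate or common.
3. Clarify when the draw takes place, since the text puts it after Visit 2 and the table marks Visits 3 to 5. Reconcile the training-stay paragraph with the end of Visit 3 on what control-first participants take home.

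The cost is some wording and a setting in the randomisation service, with no added visits or participants. Separate variances use two degrees of freedom per contrast. Late allocations become slightly more predictable in an open-label trial. Twenty is not a multiple of six, so balance is only approximate, and it weakens further if participants withdraw or visits are excluded. Balance has to be set before allocation begins.

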3.0 Statistics

From our previous published data^{1,6} we anticipate that the BiAP/ABC4D intervention will increase the percentage of time for which plasma glucose concentrations were in the target range by a mean of 6% (SD 9.9) compared with the BiAP/fixed bolus artificial pancreas system, and by an estimated mean of more than 6% (9.9) compared with the control group. We intend to do three pairwise comparisons between the interventions, and therefore have conducted a power analysis using the typical sample size formula for the paired t test. We estimate, using mean 12% (9.9), that 20 participants would provide 90% power at the 5% significance level (corrected for multiple comparisons) to detect differences between the three interventions.

Missing, unused, and spurious data will be assessed on an individual basis and may be ignored, withdrawn or the visit may be removed from the analysis with appropriate justification adjudicated by the Principal Investigator.

Efficacy

Primary outcome will be:

• % time in target range defined as 3.9-10mmol/l

Secondary outcomes will be:

- % time spent in euglycaemia (3.9-7.8mmol/l)
- % time spent in hypoglycaemia (<3.9mmol/l)
- % time spent in hypoglycaemia (<2.8mmol/l)

- % time spent in hyperglycaemia (>10mmol/l)
- % time spent in severe hyperglycaemia (<15mmol/l)
- Mean sensor glucose
- Glycaemic variability
- Glycaemic risk as measured by LBGI and HBGI
- Closed loop error grid analysis
- Glucose area under the curve
- Insulin requirement in units/kg/hr
- Hypoglycaemia awareness (Gold scores)
- Quality of life by mixed quantitative and qualitative methodologies
- Cost-effectiveness
- Device usability and acceptability
- % time in closed loop control
- Severe hypoglycaemia
- Diabetic ketoacidosis
- Sensor MAD%

These are validated, published metrics, which will be assessed at the end of each visit from CGM data. There will be an interim analysis of the data after each visit to ensure efficacy and safety.

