2.0 Clinical study

The trial will be conducted in compliance with the protocol, GCP and the applicable regulatory requirement(s).

Trial Objectives and Purpose

The main objectives of the research study is to evaluate the safety, efficacy and costeffectiveness of a bio-inspired artificial pancreas (BiAP) with, and without, the addition of an adaptive bolus calculator (ABC4D) compared to gold-standard sensor-augmented pump therapy.

Hypothesis

- 1. A bio-inspired artificial pancreas (BiAP) device has a positive impact on glucose control, as measured by time in target after 6 weeks of use, when compared with sensor-augmented pump with low-glucose suspend (LGS).
- 2. A bio-inspired artificial pancreas (BiAP) device with an adaptive bolus controller (ABC4D) has an additional positive impact on post-prandial glucose control.

Trial Design

A 3-way crossover randomized controlled trial (Fig 3). Description of the three arms:

- 1. Sensor augmented pump (open-loop)
- 2. BiAP with a fixed bolus calculator
- 3. BiAP with the Advanced Bolus Calculator for Diabetes (ABC4D)

The primary outcome from the studies will be % time spent with a glucose concentration in the target range (3.9-10.0mmol/l). This outcome incorporates safety as it ensures participants do not have low or high glucose excursions and is the principal measure of efficacy for closed-loop insulin delivery systems in the scientific literature. Other measured outcomes will be % time spent in euglycaemia (3.9-7.8mmol/l), % time spent in hypoglycaemia (<3.9mmol/l), % time spent in hyperglycaemia (>10mmol/l), mean venous blood and sensor glucose, glycaemic variability as measured by standard metrics (SD, CONGA, LI, JINDEX, GRADE, MODD, MAGE, ADDR, MVALUE, MAG), glycaemic risk as measured by low blood glucose index (LBGI) and high blood glucose index (HBGI), closed-loop error grid analysis, glucose area under the curve. All measures have been previously published and validated. Quality of life, treatment satisfaction and device acceptability outcomes will be measured using mixed methods (questionnaires and semi-structured interviews).

Methodology Randomised controlled cross-over open label study

Timescale It is anticipated that the study will take 1 year, each subject will be in the study for up 6 months, with a total of 6 visits in that timeframe.

Population

n = 20

Inclusion criteria

- Adults over 18 years of age

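### The 90% power figure rests on a 12-point difference assigned to no comparison; for the anticipated 6-point ABC4D versus fixed-bolus difference, power is about 54% if 9.9 is the SD of paired differences

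*Combined protocol and SAP*

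**What the plan says.** All the inputs are in the opening paragraph of section 3.0 Statistics of the combined protocol and SAP.

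- BiAP/ABC4D versus BiAP/fixed bolus: time in target is expected to rise "by a mean of 6% (SD 9.9) compared with the BiAP/fixed bolus artificial pancreas system".
- BiAP/ABC4D versus control: it is expected to rise "by an estimated mean of more than 6% (9.9) compared with the control group".
- BiAP/fixed bolus versus control: no anticipated difference is given. Yet hypothesis 1 in section 2.0 concerns the effect of BiAP "as measured by time in target after 6 weeks of use, when compared with sensor-augmented pump".
- Method: three pairwise comparisons are planned, and the authors "conducted a power analysis using the typical sample size formula for the paired t test".
- Result: "We estimate, using mean 12% (9.9), that 20 participants would provide 90% power at the 5% significance level (corrected for multiple comparisons"), and this power is claimed "to detect differences between the three interventions".

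The paragraph does not say which comparison the 12 points refer to or where they come from. It also leaves open whether 9.9 is the SD of paired differences or of one treatment period, whether the test is one- or two-sided, and how the correction is made.

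**The concern.** The power sentence uses double the effect anticipated earlier in the same paragraph, and then claims its result for the comparisons in general. The three differences are linked: ABC4D minus control equals ABC4D minus fixed plus fixed minus control. They cannot all be 12. Whichever comparison with control the 12 points belong to, ABC4D versus fixed bolus stays at the stated 6.

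That comparison isolates the adaptive bolus calculator and is the only one with an exact anticipated effect. If its real power is far below 90%, a non-significant result is quite likely even when the anticipated benefit is real, and it could be misread as evidence that ABC4D adds nothing. A reader cannot tell from the plan which comparisons the trial is sized to answer.

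**Working it through.** **Inputs from the plan.** n = 20 (section 2.0, Population); differences of 6 and 12 points, SD 9.9, three comparisons, 5% level corrected, paired t test (section 3.0).

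**Assumptions, because the plan is silent.** Two-sided test; Bonferroni correction, so alpha = 0.05/3 = 0.0167; no dropout.

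**Formula.** Noncentrality = (difference / SD of differences) × √n, with n − 1 = 19 degrees of freedom. The critical t at 0.05/6 per tail is 2.625. Power is the upper-tail probability of the noncentral t beyond that value. For a per-period SD with within-person correlation r, the SD of differences is 9.9 × √(2(1 − r)).

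**Step 1: can the stated 90% with 20 participants be reproduced at 12 points?**

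- *9.9 as the SD of paired differences.* Noncentrality = 12/9.9 × √20 = 5.42, and power is 99.5%. Thirteen participants suffice for 90%. The normal formula gives (2.394 + 1.282)² × 9.9²/12² = 9.19, so 10. The stated figure is not reproduced.
- *9.9 as a per-period SD, r = 0.* SD of differences = 9.9 × √2 = 14.0 and noncentrality = 3.83. Power is 87.4% (22 needed for 90%). The normal formula gives 92.5% and 18.39, so 19. A two-sample t test with 20 observations per condition gives 90.2%. This comes close to the stated figure, but only by giving up the benefit of pairing.

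**Step 2: power at the anticipated 6 points with 20 participants.**

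| Meaning of 9.9 | Noncentrality | Power at 6 | Power at 12 |
|---|---|---|---|
| SD of paired differences | 2.71 | 54.4% | 99.5% |
| Per-period SD, r = 0 | 1.92 | 26.8% | 87.4% |

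The two-sample calculation that matches 90% at 12 points gives 29% at 6.

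**Step 3: do looser error rates rescue 6 points?** With 9.9 as the SD of paired differences, power is 66% at one-sided 0.05/3, 73% at two-sided 0.05 and 83% at one-sided 0.05. None reaches 90%.

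**Step 4: does within-person correlation rescue it?** If 9.9 is a per-period SD, power at 6 points is 27%, 36%, 54% and 87% for r = 0, 0.25, 0.5 and 0.75. It reaches 90% at r of about 0.77, where the SD of differences is about 6.7. The plan gives no correlation.

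**Step 5: what can 20 participants detect?** With 9.9 as the SD of paired differences, about 8.8 points at 90% power and 7.8 at 80%. Ninety per cent power at 6 points would need 40 participants, or 31 without correction. With a per-period SD and r = 0, the difference detectable at 90% is about 12.5 points.

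**Step 6: BiAP/fixed bolus versus control (illustration only).** Keep ABC4D versus fixed at 6 and the SD of differences at 9.9. If ABC4D versus control is 12, fixed versus control is 12 − 6 = 6, with 54% power. If it is 9, fixed versus control is 3, with 13% power. Power of 90% needs about 6 + 8.8 = 14.8 points for ABC4D versus control.

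**The case against.** Four points can be made for the plan.

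- *The 90% can be approximately recovered,* so this may be no slip of arithmetic. That is fair: with a per-period SD and no credit for pairing, 20 per condition gives 90.2% at 12 points. But the plan says it used the paired formula, and on this reading power at 6 points falls to 27–29%. The 54% is the more favourable of the two results.
- *The single figure of 54% depends on an input that cannot be recovered.* This stands. The wording, a mean difference followed by its SD, favours the SD of paired differences; the arithmetic favours a per-period SD. The answer should be read as conditional, and the range in step 4 belongs with it.
- *Twelve points may simply mean 6 + 6 for ABC4D versus control,* which fits the more-than-6 expectation. This is plausible but unstated, and it leaves the other two comparisons at 6 points each.
- *Hypothesis 2 concerns post-prandial control, so ABC4D versus fixed bolus on overall time in target is not the main question.* This lowers the weight somewhat. It does not remove the point, because section 3.0 itself anticipates 6 points in time in target for that comparison and includes it among the three it claims to power.

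**Conclusion.** The concern holds. As written, the plan claims a power that the design does not have for ABC4D versus fixed bolus. Assuming a two-sided paired t test, alpha 0.05/3, no dropout and 9.9 as the SD of paired differences, power at 6 points is 54%. A true effect of that size would be missed in about 46% of such trials, not the 10% implied. If 9.9 is a per-period SD, power ranges from 27% with no within-person correlation to 87% at 0.75, and reaches 90% only at about 0.77. For BiAP/fixed bolus versus control, power cannot be judged because no difference is anticipated. This must be corrected, since the paragraph is the only sample-size justification for the primary outcome.

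**What to change.** Keep n = 20 and rewrite the power paragraph by comparison.

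1. Say which comparison the 12 points describe and where they come from.
2. Say whether 9.9 is the SD of paired differences or of one period; if the latter, give the assumed within-person correlation.
3. State the sidedness and the correction method.
4. Give an anticipated difference for BiAP/fixed bolus versus control.
5. Report power for each of the three comparisons.

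If the sponsor confirms that 9.9 is the SD of paired differences, the text could read: *Twenty participants give 90% power (two-sided paired t test, alpha 0.05/3, SD of paired differences 9.9) for a difference of about 8.8 points; power for the anticipated 6-point difference between BiAP/ABC4D and BiAP/fixed bolus is about 54%.* If 9.9 proves to be a per-period SD, these figures must be recalculated first.

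Optionally, the correction could be replaced by a closed procedure for three arms: an overall treatment test at 5%, then each pairwise test at 5%. In simulation with equal variances and correlations and an SD of differences of 9.9, power at 6 points was about 68–73%, which is better but still below 90%.

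The cost is protocol and SAP wording and a less favourable stated power. No participants or procedures are added.

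### Data and visits can be excluded case by case in an open-label trial, with no objective criterion, masking, by-arm report or full-data analysis

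*Combined protocol and SAP*

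**What the plan says.** The only exclusion rule is in section 3.0 Statistics: "Missing, unused, and spurious data will be assessed on an individual basis", and such data "may be ignored, withdrawn or the visit may be removed from the analysis with appropriate justification adjudicated by the Principal Investigator". A justification is therefore required and the Principal Investigator rules on it. Who proposes an exclusion is not stated.

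Three other statements bear on what is known when that ruling is made:

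- Section 2.0, Methodology, describes the trial as open label.
- Section 3.0, Efficacy, says the outcomes are metrics "which will be assessed at the end of each visit from CGM data" and adds: "There will be an interim analysis of the data after each visit to ensure efficacy and safety".
- Section 4.0 Data says the research team, including its engineers, analyses anonymised data. Anonymising removes identity; masking to arm is not mentioned.

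The document does not define spurious or unused data, a minimum CGM coverage, an analysis set or a deadline for exclusion decisions. It plans no report of exclusions by arm and no sensitivity analysis. It also does not say whether a *visit* is a clinic attendance or the 6-week period that Visits 4, 5 and 6 each close.

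**The concern.** When arm and result can both be known, a case-by-case rule allows the decision to depend on them, even in good faith. A period with many sensor gaps may look spurious in one arm and acceptable in another. Controller failure, which the Safety text in section 1.0 anticipates, belongs to closed-loop operation. Whether such time counts as unused is left open.

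All three pairwise comparisons are exposed. Removing one period takes that participant out of two of the three paired differences. A favoured direction is also stated throughout. Hypothesis 1 expects the closed loop to beat the sensor-augmented pump. Hypothesis 2 expects an added gain from ABC4D, and section 3.0 anticipates 6 points for BiAP/ABC4D over BiAP/fixed bolus.

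At stake is whether a reader of the results could tell harmless exclusions from harmful ones. As planned, nothing would be reported that lets them do so.

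**Working it through.** **Inputs from section 3.0.** n = 20; three paired comparisons; SD 9.9; anticipated gain 6 points between the closed-loop arms and "by an estimated mean of more than 6% (9.9) compared with the control group"; sizing effect 12 points; 5% level corrected for multiple comparisons. **Assumed:** two-sided Bonferroni, 0.05/3 = 0.0167, because the correction is not named; between-subject SD b from 0 to 15 points; *visit* read as a 6-week period.

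**Step 1: the plan's own figure.** The plan states: "We estimate, using mean 12% (9.9), that 20 participants would provide 90% power". Power for a paired t test uses the noncentral t with noncentrality 12 x sqrt(20)/SD of the difference.

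- If 9.9 is the SD of the difference, noncentrality is 5.42, power is 99.5% and 13 participants suffice for 90%.
- If 9.9 is the SD of one period with no within-person correlation, the SD of the difference is 9.9 x sqrt(2) = 14.0. Noncentrality is 3.83, power is 87.4% and 22 participants are needed (19 by the normal two-means formula).

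Only the second reading comes near 20, so both are carried forward. The standard errors are 9.9/sqrt(20) = 2.2 and 14.0/sqrt(20) = 3.1 points.

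**Step 2: expected shift if the k worst periods of one arm are removed.** Let w be the within-person SD of a period (9.9/sqrt(2) = 7.0, or 9.9). The two lowest of 20 standard normal values are expected at -1.867 and -1.408. With c = 1.867 for k = 1 and c = 1.867 + 1.408 = 3.275 for k = 2,

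shift = c x w² / [sqrt(w² + b²) x (20 - k)].

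- w = 7.0, k = 1: 1.867 x 7.0/19 = 0.69 at b = 0; 1.867 x 49/(16.55 x 19) = 0.29 at b = 15.
- w = 7.0, k = 2: 3.275 x 7.0/18 = 1.27 at b = 0; 3.275 x 49/(16.55 x 18) = 0.54 at b = 15.
- w = 9.9, k = 1: 0.97 at b = 0; 0.54 at b = 15.
- w = 9.9, k = 2: 1.80 at b = 0; 0.99 at b = 15.

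**Step 3: false-positive rate in that arm's favour.** This was simulated with 100,000 trials per setting, no true difference, a paired t test and upper-tail rejection at 0.0167/2.

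| SD of difference | b | none removed | one removed: shift, error | two removed: shift, error |
|---|---|---|---|---|
| 9.9 | 0 | 0.8% | 0.68, 1.9% | 1.27, 3.7% |
| 9.9 | 15 | 0.9% | 0.29, 1.2% | 0.54, 1.6% |
| 14.0 | 0 | 0.8% | 0.96, 2.0% | 1.79, 3.6% |
| 14.0 | 15 | 0.9% | 0.53, 1.3% | 0.98, 1.8% |

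The no-removal rate is 0.0167/2 = 0.8% by construction. Repeat runs widen the error ranges slightly, to 1.1-2.1% for one removal and 1.5-3.8% for two. Removing two pairs without regard to outcome gave no shift and left the error at about 0.8%.

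**Step 4: the narrow reading of *visit*.** If only the stay at Visit 3 is meant, about 1 of 42 days is lost. Suppose time in range that day differs by 10-30 points in either direction (assumed). One removal then moves that participant's period by 10/42 to 30/42 = 0.24-0.71 points, and the mean of 20 by 0.01-0.04 points. That is negligible.

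**The case against.** The strongest reply is that the illustration models a misuse of the sentence. The rule covers missing, unused and spurious data only, and asks for justification. A complete, valid but poor period is none of these. This stands: a reader might infer that the plan allows poor device periods to be dropped, but the text does not authorise it and nothing shows that it would happen. The figures show how far the result could move, not how far it will.

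A reader might also infer that the Principal Investigator alone picks what to remove. The text gives that role adjudication of the justification, and is silent on who assesses or proposes.

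A third inference comes from the treatment description in section 1.0: "The treatment periods are defined by time spent in closed-loop insulin delivery". It might suggest that time with the loop off is left out of the analysis. The document does not support that. The sentence is not an analysis rule. Hypothesis 1 measures time in target after 6 weeks of use, and the secondary outcome of percentage "time in closed loop control" would be 100% by definition if loop-off time were dropped.

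Safeguards do exist. Source data are open to monitoring and audit. Study Management provides monthly data reviews and a data monitoring committee with statistical expertise. Section 5.0 postpones visits during intercurrent illness, which removes one ordinary reason to discard a period. The Consent text keeps participants given alternative treatment in the analysis. These lower the risk, but none says which readings or periods count, so an auditor would have no rule to check against.

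**Conclusion.** The concern holds in a limited form. Exclusions rest on individual judgement that can be made knowing arm and outcome, and the plan would report nothing from which a reader could judge them. This follows from the text and does not depend on the simulation.

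The possible size is modest. With *visit* read as a 6-week period, removing the worst one or two periods of one arm moves the mean by about 0.3-0.7 or 0.5-1.3 points if 9.9 is the SD of the difference. If it is the per-period SD, the shifts are about 0.5-1.0 or 1.0-1.8 points. The largest, 1.8, is 30% of the anticipated 6 points and 15% of the 12 used for sizing, and is below one standard error. Upper-tail error rises from about 0.8% to about 1.1-2.1% or 1.5-3.8%. These figures assume outcome-driven removal, Bonferroni and a between-subject SD of 0-15.

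This is a cheap improvement that should be made. It is not evidence that the result will be biased.

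**What to change.** Replace the exclusion sentence in section 3.0 with four statements:

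1. Readings or periods are excluded only by objective criteria, namely sensor-error criteria and a minimum CGM coverage. The sponsor sets the values, which are fixed before any comparison between arms and applied without arm labels.
2. Exclusions and their reasons are reported by arm.
3. A sensitivity analysis of the primary outcome includes every allocated period with CGM data.
4. The plan states whether *visit* means a clinic attendance or a 6-week period.

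The cost is new wording and a little more analysis work, with no new data or visits. The downside is that fixed criteria may keep some spurious readings that individual review would have caught.
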